### PK Collection

- The CRC will weigh the cigarette butt after smoking is complete.

### Ad Lib Use

- CRC will provide tobacco cigarettes based on participant's normal brand and cigarettes per day
- CRC will weigh a standard reference tobacco cigarette before ad lib begins
- CRC obtains final weight of all tobacco cigarette butts
- At the end of the day, **final questionnaires** will be administered: Overall Drug Liking Assessment, GRPQ for tobacco cigarettes
- Regardless of which product was assigned, on Hospital Study Visit 2, the participant will also take the following as part of their final questionnaires: Difficulty Quitting, Purchase Tasks, Stiles Intent to Use Product Again

## 6.7 PARTICIPANT COMPENSATION

Below describes the participant compensation schedule for this study.

	Screening Visit	COVID-19 RT PCR Test	Hospital Study Visit 1	Hospital Study Visit 2	Completion Bonus
Compensation	\$30	\$20	\$350	\$350	\$100
Type	Check	Check	\$300 – check \$50 – cash (for Expired CO ≤5ppm)	\$300 – check \$50 – cash (for Expired CO ≤5ppm)	cash
Processing Time point	After saliva cotinine results	After COVID test result	In final check (unless dropout)	In final check	At end of final visit
Total possible compensation	\$30	\$50	\$400	\$750	\$850

## 7 DUTIES AND RESPONSIBILITIES OF STAFF

The Principal Investigator is responsible for study design and oversight of implementation, data analysis, and manuscript preparation.

The Co-Principal Investigators are responsible for study design and oversight of implementation, data analysis, and manuscript preparation, with the assistance of the Principal Investigator.

The Medical Monitor is responsible for medical study chart review and eligibility determination, medical history and physical examination at ZSFG admissions, reviewing and determining relatedness of adverse events, and other medically related expertise.

The Clinical Research Coordinator will oversee study logistics including consenting and screening participants, conducting study visit procedures, coordinating outpatient admissions and procedures with nursing staff at the research ward, coordinating specimen testing with laboratory, overseeing participant reimbursement, maintaining study charts and data entry.

Statistical Analysis Plan: Evaluating the Comparative Pharmacokinetics of Nicotine after administration via JUUL or Tobacco Cigarettes

June 9, 2020

Protocol Number: 19-28309

Grant Number: R01DA039264

[name] (PI)

[name], PhD (Co-I)

Summary of Protocol

Description and Outcome Measures

This is an observational, crossover design that will examine the pharmacokinetics and pharmacodynamics of smoking tobacco cigarettes compared to vaping the JUUL electronic cigarette. Participants will be recruited in two groups: primary e-cigarette vapers and primary cigarette smokers. The order of assignment to either tobacco cigarettes or the JUUL electronic cigarette will be counter-balanced. We will seek to enroll 30 participants total (15 in each group).

The following schedule of events describes the study procedures:

Study Day – Tobacco Cigarette Condition	Study Day – JUUL E-Cigarette Condition
Day 1	Day 2
←----- HOSPITAL -----→	

• Baseline Blood Draws
• 1 nicotine 6ml blood draw• 1 catecholamine 6ml blood draw• Baseline Urine Nicotine and VOCs• Baseline Heart Rate• Baseline Blood Pressure• 1st Standardized Session• 2-hr abstinence and biological samples and measurements
• 9 nicotine 6ml blood draws• 12 heart rate measurements• 10 blood pressure measurements• 1 urine sample• 1 catecholamine 6ml blood draw• 4-hr recorded ad libitum use and biological samples and measurements
• 8 nicotine 6ml blood draws• 1 urine sample	
• Baseline Blood Draws
• 1 nicotine 6ml blood draw• 1 catecholamine 6ml blood draw• Baseline Urine Nicotine and VOCs• Baseline Heart Rate• Baseline Blood Pressure• 1st Standardized Session• 2-hr abstinence and biological samples and measurements
• 9 nicotine 6ml blood draws• 12 heart rate measurements• 10 blood pressure measurements• 1 urine sample• 1 catecholamine 6ml blood draw• 4-hr recorded ad libitum use and biological samples and measurements
• 8 nicotine 6ml blood draws• 1 urine sample

Power Calculation & Sample Size

Our power analysis based on a 2-condition within-subject repeated measures comparison. To estimate the required sample size the minimal power level was set at 80% and Type I error at 0.05, with use of a 2-sided test. The primary outcome on which we have powered the study is the difference in nicotine exposure for JUUL vs tobacco cigarette use. We used prior within-subject variability data on plasma cotinine (mean 200 ng/ml, coefficient of variation, COV 25%) in TC smokers whose cotinine had been measured on multiple occasions for estimation. For 15 participants, we have 80% power to detect an effect size ratio of 1.25 for daily nicotine exposure.

[figure not shown]
Trial Management

Study Site & Timetable

Participant visits will be conducted at Zuckerberg San Francisco General Hospital (ZSFG) at both the Tobacco Research Center and the Clinical Research Services Research Ward.

The projected study timetable is as follows:

Timeline	Specific Aim
Preparation (Months 1-2)	
• Study startup (supply purchasing, case report form and database completion)• Clinical Research Coordinator & CTSI staff training• Participant Recruitment
Clinical Study (Months 3-12)	
• Recruit, enroll and complete study procedures on approximately 2-4 participants per month• Conduct online analytical chemistry assays• Conduct ongoing data entry and quality assurance
Analysis (Months 9-12)	
• Complete data entry, analysis and manuscript preparation• Complete analytical chemistry assays

Targeted Population

We will seek to complete a total of N=30 randomized participants. We will seek to enroll equal numbers of men and women, and all minority groups will be invited to participate. At a minimum we will enroll 25% women in the sample (about N=5). We will not enroll minors or those under tobacco purchasing product age (21 years) in the state of California.

Data Acquisition and Transmission

Data capture will occur in several ways. Identifying information will be stored locally at UCSF in a secure database and/or locked secure files. General recruitment and enrollment information, such as dates of screening and enrollment will be stored in a password protected Excel database supported by Information and Technology (IT) at UCSF.

Data will be acquired via participant self-report and in a combination of paper source documentation transcribed into electronic data capture (EDC) by clinical research staff, and by direct entry into EDC by participants. Medical history data will be collected as paper source and will remain paper source and not entered. Demographics, nicotine & tobacco product use, drug use and nicotine dependence recorded at baseline will be entered by the participant directly into EDC, and there will be no paper source files. Physiological measures such as blood pressure, urine tox and pregnancy test results will

be recorded on a paper CRF and entered into the EDC. Adverse events will be recorded on an AE log. This paper source log will be entered into the EDC. Questionnaires completed during the study on craving, satisfaction and emotions will be entered by the participant directly into EDC. Cardiovascular data will be downloaded from the ambulatory blood pressure monitor into a PDF, which will be transcribed into Excel and uploaded directly into EDC. Video files from the recorded adlib sessions will be transferred from the camcorder to an encrypted hard drive that will be stored in a secured locked cabinet accessible by study staff only. All source documents will be stored in participant binders. Data management activities will be performed using REDCap.

REDCap is a suite of software tools, supported by UCSF, which enables the collection, cleaning and viewing of clinical trial data. The database will be designed by the study team and once approved by the Investigator, Statistician, and Clinical Research Coordinator (CRC), the database will be put into production and data entry will begin. Data can be entered and changed only by those with the rights to do so. Varying interfaces allow for the CRC to view and enter data in a database format, and for the research participant to respond to questionnaires directly through electronic data capture.

REDCap has all capability to be compliant with 21CFR Part 11 and all relevant technical aspects of relevant GCP guidelines and allows for the following:

- The system can generate accurate copies of stored data and audit trail information in human readable form.
- System access is limited to authorized individuals through the controlled assignment of unique ID and password combinations.
- The system is designed to periodically force users to change their passwords and verifies that user ID and password combinations remain unique.
- The system automatically generates a permanent time-stamped audit trail of all user interactions.
- The system allows for automated field calculations, basic validation checks and double data entry comparisons.

When data entry is complete, all data will be reviewed for any missing, incomplete, or invalid data points for resolution by the Clinical Research Staff and Investigator. Once all queries have been resolved, the data can be released to the statistician for analysis.

Research data will be protected and maintained by:

- Data files (and data link files) will be stored in a password-protected, secure network folder. All data files that are created and shared with the study

investigators will be encrypted and password-protected.

- Access to the data by all necessary research personnel will be through a password-protected network computer. At no time will data be downloaded on a thumb drive or other portable media or laptop. Subject identity will not be disclosed in the event of publication or sharing of data.
- Any paper files containing identifiers (if applicable to the research) will not be taken off UCSF premises; they will be kept in a locked filing cabinet in a secure building.
- Video files will not be transferred or stored on any non-encrypted devices and the hard drive containing the video files will not be taken off UCFS premises; the drive will be stored in a locked cabinet in a secure building.
- Subject identity will not be disclosed in the event of publication or sharing of data.
- PHI will be not re-used or disclosed for purposes other than research use.
- There are no outside entities to which PHI will be disclosed.

To ensure adherence to ethical practices, it will be made clear to participants that all information obtained during assessments is confidential and that no information will be shared with the participants' clinicians or others unless the participant requests this in writing and signs a HIPPA form. All investigators and staff associated with this study have been trained, and new hires will be trained, on human research ethics and Good Clinical Practice in accordance with the requirements of UCSF during initial study approval.

The first step in the analysis will be examining the collected data using graphical analysis and descriptive summaries to ensure that all are within expected ranges, to check for the presence of outliers and abnormal values, and to ascertain that the distribution of all measures meets the assumptions of the statistical tests to be used. Means of the outcome measures will be tested for equality using a repeated measures model. Tests will include, in addition to treatment condition, a test for order to determine possible carry-over effects. Estimation will be done using full-information maximum likelihood methods so that we can use all data in estimation even if some are missing. Analyses will primarily be conducted using SAS 9.4. More specifically, the analyses for each sub-aim are described below:

Specific Aim 1: We will determine from the standardized sessions the plasma nicotine peak concentration, time to peak concentration and area under plasma nicotine concentration-time curve (AUC) and compare JUUL vs. tobacco cigarette conditions using a mixed-effect

model for cross-over. We will also compute ratios of AUC values for the two conditions, as is commonly done in comparing the pharmacokinetics of different pharmaceutical products. The ratio of AUCs will give us information on relative nicotine doses obtained from JUUL vs. tobacco cigarettes.

Specific Aim 2: We will perform the same analysis as Specific Aim 1, but with plasma nicotine concentrations from the ad libitum periods.

Specific Aim 3: With standardized sessions, we will use a paired t test to compare peak changes in heart rate, and changes in plasma norepinephrine and epinephrine concentration, and pulmonary function tests (FEV1, FVC, FEV1/FVC).

Specific Aim 4: Satisfaction, psychological reward, unpleasant effects and withdrawal symptoms will be compared using a mixed effects model for cross-over data average measures from the mCEQ, the QSU and the MNWS for the JUUL e-cigarette and tobacco cigarette conditions.

Quality Assurance

Procedures in place to ensure the validity and integrity of the data

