### 3.2 ENROLLMENT TARGET

We will enroll a total of 30 participants, across two groups; 15 primary cigarette smokers who may have occasionally used electronic cigarettes and 15 experienced electronic cigarette users who occasionally smoke tobacco cigarettes. We will seek to enroll equal numbers in each group, but will remain flexible during recruitment.

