### Ad Lib Use (12 PM – 4 PM)

- At approximately 12:00 PM , a 4 hour ad lib video taped session will begin and participants will be allowed to use the JUUL as they wish
- CRC will weigh the JUUL e-cigarette before ad lib begins
- **Questionnaires** administered half-way through ad lib at approximately **1:30PM**: MNWS, QSU, mCES; **5, 10, 15, 30, 45, 60, and 120 minutes** post ad lib start: Henningfield Drug Liking Assessment
- Blood samples will be collected every 30 minutes during ad lib at 12:30 PM, 1:00 PM, 1:30 PM, 2:00 PM, 2:30 PM, 3:00 PM, 3:30 PM & 4:00 PM for **plasma nicotine**
- Urine Sample will be collected at 195 minutes into Ad Lib session
- **Final questionnaires** administered at 3:50 PM: MNWS, QSU, mCES, Overall Drug Liking Assessment, GRPQ for JUUL, Utility of E-Cigs Questionnaire
- CRC obtains final weight of JUUL e-cigarette
- At 4:00pm the participant is discharged from the hospital ward

## 6.6 HOSPITAL STUDY DAY 2

In most cases, hospital study day 2 will occur directly after study day 1, however if it is more convenient for the participant to reschedule to a later time, they can complete study day 2 between 2 days and up to one week from study day 1. **The below describes procedures if Hospital Study Day 1 assignment was the JUUL vaping.**

The tobacco cigarette ARM will differ from the JUUL e-cigarette ARM in the following ways:

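### The crossover analysis never names a period (Day 1/Day 2) effect, and Aim 3's paired t test cannot hold one: precision is lost at the planned 15/15 split, and bias enters only if the sequences become unequal

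*SAP*

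**What the plan says.** The opening paragraph of the SAP's Data Analysis Plan sets the general approach: "Means of the outcome measures will be tested for equality using a repeated measures model". It then names what will be tested: "Tests will include, in addition to treatment condition, a test for order to determine possible carry-over effects". On missing data it adds: "Estimation will be done using full-information maximum likelihood methods so that we can use all data in estimation even if some are missing".

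The aims follow. For Aim 1 the SAP will "compare JUUL vs. tobacco cigarette conditions using a mixed-effect" model for cross-over, and Aim 2 repeats that analysis on the ad libitum data. Aim 4 outcomes are to be "compared using a mixed effects model for cross-over data average measures" from the questionnaires. No list of fixed effects is given for any of these. Aim 3 is different: "we will use a paired t test to compare peak changes in heart rate", and the same test serves catecholamines and lung function.

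Period 1 and Period 2 appear as column heads in the allocation table of Protocol section 6.3. No analysis text in either document names a period, day or visit effect.

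**The concern.** In a two-product, two-day crossover, a test of order aimed at carry-over is the contrast between the JUUL-first and tobacco-first sequences. That contrast lies between participants. It removes nothing from the within-person product difference if everyone's values move between Day 1 and Day 2, for example through familiarity with the ward or with a device supplied only about a day before admission (Protocol section 6.3).

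A shift that is not modelled has two possible consequences. With equal sequences it cancels from the estimate but stays in the residual, so intervals are too wide and the test is conservative. With unequal sequences part of it also enters the product contrast. Visit day is recorded anyway, so both can be avoided.

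If order was instead meant as visit day, the shift is removed, but the term is then not a test of carry-over. The sentence needs correcting on either reading.

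**Working it through.** **Inputs from the documents**
- Two-sided alpha 0.05, CV 25% (plasma cotinine), ratio 1.25, 15 participants, 80% power: SAP, Power Calculation & Sample Size.
- Allocation list, Protocol section 6.3, counted as JUUL-first/tobacco-first: first 15 rows 8/7, first 30 rows 15/15, all 40 rows 20/20. It is a single list, not split by user group.

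**Assumptions**
- Analysis on the log scale, with the cotinine CV applied to the nicotine measures.
- A Day 2 minus Day 1 shift π of 0.1 or 0.2 on the log scale (exp(0.1) = 1.105 and exp(0.2) = 1.221, called 10% and 22% below).

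**The plan's own figure.** On the raw scale the SD of a paired difference is √2 × 25% of the mean, so a 25% difference has standardized size 1/√2 = 0.707. The normal approximation gives Φ(0.707 × √15 − 1.96) = 78.2%, close to the stated 80%. A paired t test gives 72.2%. This figure neither uses nor mentions a period term, so it does not settle the question.

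**Effect of leaving period out.** Let d be the JUUL-minus-tobacco difference with true mean τ. Its mean is τ − π in JUUL-first participants and τ + π in tobacco-first participants. With nA and nB participants in the two sequences, N = nA + nB and p = nA/N:
- the unadjusted estimate has mean τ + π(nB − nA)/N;
- Var(d) rises by 4p(1 − p)π².

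A sequence main effect changes neither result. Simulated mixed models agree: at 15/15 with π = 0.20 and a true residual variance of 0.0625, treatment plus sequence gave no bias and a residual variance of 0.082, against 0.061 once period was added.

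**Planned split, 15/15.** SD of d = √(2 ln(1 + 0.25²)) = 0.348. Bias = π × 0/30 = 0. Standard error inflation = √((0.348² + π²)/0.348²) = 1.04 or 1.15. Simulated t tests gave:

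| Shift | Size, no period term | Power for 1.25, no period term | Power with period term |
|---|---|---|---|
| none | 5% | 92% | 92% |
| 10% | 4.2% | 91% | 92% |
| 22% | 2.5% | 87% | 92% |

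Repeat simulations ranged from 4.1% to 4.2% and from 2.2% to 2.5% for size.

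**Unequal sequences.** The share of π that becomes bias is |nB − nA|/N: 1/15 = 6.7% at 8/7, 2/28 = 7.1% if two participants drop out of one sequence (15/13), and 5/15 = 33% at 10/5. At 10/5 the ratio is off by exp(0.1/3) − 1 = 3.4% or exp(0.2/3) − 1 = 6.9%, and simulated type I error is about 5.5% or 6.4%, against 5% with period in the model.

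**How likely is 10/5?** Suppose the 15/15 list falls at random across two groups of 15. The chance that a given group is 10/5 or worse is 2 × Σ(k ≥ 10) C(15,k)·C(15,15−k)/C(30,15) = 14%. For 9/6 or worse it is 47%, and for 11/4 or worse 2.7%. The other group is then the mirror image, so the pooled split stays 15/15.

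**The case against.** **The model may already contain period.** A mixed model for cross-over data is often understood to include period. The sentence naming treatment and order does not claim to be a full model statement, and an order-by-treatment interaction in a two-by-two design is the period effect. This stands for Aims 1, 2 and 4: the defect there is an unspecified term, not a demonstrably wrong model. It does not help Aim 3, where a paired t test has no place for the term.

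**The planned analysis is unbiased.** This also stands. The list is 15/15 at 30, the unadjusted test errs on the conservative side, and power stays above the 80% target even at a 22% shift. At 10% or less the pooled effect is small.

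**Stronger readings that the documents do not support.**
- A reader might infer that the product comparison is biased as planned. It is not at 15/15. Bias requires drop-out that unbalances the sequences or an analysis within a user group, and the SAP describes no separate analysis by group; only the power statement for 15 participants hints at one.
- A reader might point to an inflated type I error of about 11%. That needs an 11/4 split together with a 22% shift, and 11/4 or worse has only about a 2.7% chance in a given group.
- Protocol section 3.2 says: "We will seek to enroll equal numbers in each group, but will remain flexible during recruitment". This concerns smokers and vapers, not the two sequences.
- Protocol section 6.6 says: "In most cases, hospital study day 2 will occur directly after study day 1". This is about spacing, which bears on carry-over; it is not evidence of a period shift.

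**Conclusion.** The point holds in a limited form. The SAP leaves period unnamed for Aims 1, 2 and 4 and excludes it by choice of test for Aim 3. If all 30 complete at 15/15, the cost is precision alone: about 1 or 5 points of power (92% to 91% or 87%) for shifts of 10% or 22%. Bias is conditional on unequal sequences and moderate at 10/5. Full-information maximum likelihood keeps incomplete participants in the analysis but does not stand in for a period term.

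The sizes rest on shifts that the documents do not give and on a cotinine CV that may not match nicotine peak or AUC in these sessions. They do not carry over directly to Aim 3's heart rate, catecholamine and lung-function outcomes, although the algebra does. The change is worth making because it is nearly free at the planned split, not because the planned result would otherwise be invalid.

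**What to change.** For Aims 1, 2 and 4, state the fixed effects as product, period (Day 1/Day 2) and sequence, with participant as a random effect, and take the product contrast and its interval from that model. Say whether the order test means sequence or visit day. For Aim 3, replace the paired t test with the same model, or with a period-adjusted comparison of within-person differences (the average of the two sequence-specific means).

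The cost is a few lines of SAP text and one degree of freedom; no new data are needed. If there is truly no period effect, power for a ratio of 1.25 falls by under 1 point at 15/15 or 8/7, by about 6 points at 10/5 (64% to 58%) and by about 11 points at 11/4 (64% to 53%).

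### The SAP fits its crossover mixed models by full-information maximum likelihood, which at n = 30 makes the product-contrast standard error about 1.7% to 3.4% too small

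*SAP*

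**What the plan says.** The opening paragraph of the SAP's Data Analysis Plan, which precedes the aim-by-aim methods, states: "Estimation will be done using full-information maximum likelihood methods so that we can use all data in estimation even if some are missing". It is the only estimation rule in either document.

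- **Aims 1 and 2** (peak concentration, time to peak and AUC, in the standardized and ad libitum sessions): the SAP will "compare JUUL vs. tobacco cigarette conditions using a mixed-effect" model for crossover data.
- **Aim 4** (satisfaction, reward, unpleasant effects, withdrawal): these outcomes "will be compared using a mixed effects model for cross-over data average measures" from the questionnaires.
- **Aim 3** (heart rate, catecholamines, pulmonary function): "we will use a paired t test to compare peak changes in heart rate" and the other outcomes, so no mixed model is involved.

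On model terms, the SAP says: "Tests will include, in addition to treatment condition, a test for order to determine possible carry-over effects". It does not name a period effect or a group-by-product term.

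Under Targeted Population: "We will seek to complete a total of N=30 randomized participants". Under Power Calculation & Sample Size, the planning value is "Type I error at 0.05, with use of a 2-sided test". The software is SAS 9.4. REML, a small-sample correction, a degrees-of-freedom method and a SAS procedure are not mentioned.

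**The concern.** ML estimates a variance by dividing the residual sum of squares by the number of observations, with no deduction for the fixed effects estimated from the same data. In large trials this is negligible. In a crossover with 30 participants it is small but visible: standard errors come out too small, confidence intervals too narrow and p values too low. REML makes the deduction.

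The SAP's reason for choosing ML is missing data. That does not separate the two methods, because REML uses the same incomplete records under the same missing-at-random assumption. The plan therefore accepts a type I error somewhat above its own 5% and gains nothing for it.

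The aims are also treated unevenly. The paired t test in Aim 3 divides by n − 1 and holds its level. With complete data and product as the only within-participant effect, REML would reproduce that paired t test; ML does not. The nicotine exposure comparisons, the kind of outcome on which the study was powered, fall to the ML-fitted models.

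**Working it through.** **The plan's own figures.** The documents give no standard error or ML bias to reproduce. Their nearest figure is 80% power for 15 participants to detect a ratio of 1.25 (mean 200 ng/ml, CV 25%). On the raw scale, the within-participant SD is 50, the SD of a difference is 50 × √2 = 70.7 and the target difference is 50. A paired normal approximation gives power Φ(50 / (70.7/√15) − 1.96) = Φ(0.779) = 78.2%, close to the stated value. This does not bear on the choice of estimator.

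**Inputs for the check.**
- n = 30 participants (SAP, Targeted Population), all with both periods.
- Two periods per participant, in sequence JUUL–tobacco or tobacco–JUUL (Protocol, Design Summary and the Latin square table under Orientation).
- p = number of within-participant fixed effects. Sequence is a between-participant term and does not count. If order in the SAP means sequence only, p = 1 (product). If a period effect is fitted, p = 2.
- Two-sided 0.05 (SAP, Power Calculation & Sample Size).

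**Step 1: standard error.** With complete data the product contrast rests on within-participant differences. ML divides their residual sum of squares by n, and REML divides it by n − p. Hence

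SE(ML) / SE(REML) = √((n − p)/n).

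- p = 1: √(29/30) = 0.983, so 1.7% too small.
- p = 2: √(28/30) = 0.966, so 3.4% too small.

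**Step 2: actual type I error.** An ML-based t statistic is inflated by 1/ratio, so a test against the usual t critical value has level 2 × P(t with n − p df > t_crit × ratio).

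- p = 1: 2.045 × 0.983 = 2.011 on 29 df, giving 0.0537.
- p = 2: 2.048 × 0.966 = 1.979 on 28 df, giving 0.0577.

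**Step 3: what a borderline result becomes.** A result whose correct p value is 0.050 is reported as 2 × P(t > t_crit/ratio).

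- p = 1: 2.045 / 0.983 = 2.080, giving 0.046.
- p = 2: 2.048 / 0.966 = 2.120, giving 0.043.

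**Step 4: checks by simulation.**

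| Check (n = 30) | ML | REML |
|---|---|---|
| Level, p = 1, 200,000 trials | 0.0537 | 0.0501 |
| Level, p = 2, 200,000 trials | 0.0577 | 0.0499 |
| Level, full mixed model, complete data, 5,000 trials | 0.060 | 0.052 |
| Level, full mixed model, 3 second-period records missing, 5,000 trials | 0.064 | 0.055 |

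The full mixed models had a random participant effect, fixed effects for product, period and sequence, and equal between- and within-participant variances. The Monte Carlo standard error of their levels is 0.003. Their mean ML/REML standard error ratio was 0.966 with complete data and 0.963 with three records missing. The three missing records are an assumption, and those tests used a t reference on complete pairs minus 2 degrees of freedom, not Kenward-Roger. Separate ML and REML fits to simulated 30-participant crossovers gave shortfalls of 1.68% for product alone, 1.68% for product plus sequence, and 3.39% once period was added.

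**Step 5: cases outside the stated plan.** These need assumptions that the SAP does not make.

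| Case | SE ratio | Level |
|---|---|---|
| n = 30; product, period, group-by-product (p = 3) | 0.949 | 6.2% |
| One group of 15 alone; product and period | 0.931 | 6.6% |
| n = 30; product and period; normal critical value 1.96 | 0.966 | 6.9% |

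**The case against.** The strongest reply is that full-information maximum likelihood may be loose shorthand for a likelihood-based analysis of all available records. The sentence's own purpose clause is about missing data, and no SAS procedure or estimation option is named. On that reading nothing is biased and only the wording needs repair. This reading is possible, but the literal one is the natural one. Either way the SAP has to name its estimator.

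Second, the 3.4% figure needs a period effect that the SAP does not name. On the terms it does name, with order read as sequence, the shortfall is 1.7% and the level 5.4%. That is correct, and it is why the size is given as a range. A crossover mixed model may well include period, but the text does not settle it.

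Third, the effect is small. It adds 0.4 to 0.8 percentage points per test, in a plan with many outcomes and no stated multiplicity control. With complete data the estimates themselves do not change. This stands, and it keeps the point minor.

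Fourth, the benefit of the fix is shown most clearly for complete data. With three records missing, REML with the simple t reference gave 0.055, not 0.050. That is better than 0.064 for ML and within two Monte Carlo standard errors of 0.050, but Kenward-Roger itself was not simulated.

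**Conclusion.** The concern holds, as a minor one. Under ML as written, with 30 complete participants, the product-contrast standard error is 1.7% too small (product the only within-participant effect) to 3.4% too small (product and period), and t-based tests run at 5.4% to 5.8%. Only borderline results in Aims 1, 2 and 4 would change.

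The conclusion rests on three assumptions: ML is meant literally as the variance estimator, all 30 participants supply both periods, and tests use a t reference. The larger figures, 6.2% to 6.9%, belong to analyses that the SAP does not specify and should not be read as the size of the present problem.

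**What to change.** Replace the estimation sentence in the Data Analysis Plan with:

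> Mixed models will be fitted by restricted maximum likelihood (SAS PROC MIXED, METHOD=REML) with Kenward-Roger degrees of freedom, using all available observations. Fixed effects are product, period and sequence; participant is a random effect.

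The first sentence removes the bias and keeps the incomplete records. The second is a separate specification point, but it is needed because the SAP does not say whether order includes period, and that determines the degrees of freedom.

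The cost is two SAP sentences and one software option, with no extra data. The price is that p values, and any confidence intervals reported, become slightly less favourable.
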